4.3 Randomization and Blinding

This is an observer-blinded clinical study. Both the study subjects and the study personnel involved in safety assessment (observers) will be blinded to treatment assignments. Designated unblinded study-site personnel will be responsible for preparing and administering the study injection.

In Part 1, subjects will be randomized 1:1:1 to Group 1, 2, or 3. In Part 2, subjects will be randomized 1:1 to 1 of 2 groups (ie, either Group 1 and 3 or Group 2 and 3) as determined from Part 1. Randomization will be stratified by site.

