11.4 Immunogenicity Endpoints

The primary and other immunogenicity endpoints will be analyzed using the mITT population. Sensitivity analyses on immunogenicity data will also be presented using the PP population.

Immunogenicity will be measured by serum rF1V [REDACTED] concentration at each visit.

Part 2 Primary Objective 1: To assess the utility of a 2-dose schedule of rF1V vaccine with CpG 1018 as measured by reduction in time to onset of predicted rF1V protection

Endpoint: predicted protection (percentage of subjects reaching the [REDACTED] threshold that corresponds to 50% predicted vaccine efficacy) at Week 8 after 2 doses of rF1V vaccine with CpG 1018 as that at Week 30 after 3 doses of rF1V vaccine without CpG 1018

[figure not shown]
Percentage of subjects reaching the [REDACTED] threshold and associated 95% two-sided Clopper-Pearson confidence intervals will be computed. Fisher's exact tests will be used to compare predicted protection rate between study groups.

Criterion for evaluation: similar percentage of subjects reaching the [REDACTED] threshold that corresponds to 50% predicted vaccine efficacy after 2 doses of rF1V vaccine with CpG 1018 as compared to that after 3 doses of rF1V vaccine.

Part 2 Primary Objective 2: To assess the serum [REDACTED] concentration to rF1V vaccine with CpG 1018 compared with rF1V vaccine 28 days after the second dose of vaccine

Endpoint: Ratio of geometric mean ELISA concentration (GMC) between rF1V vaccine with CpG 1018 and rF1V vaccine at Week [REDACTED]

Criterion for evaluation: 2-times increase in [REDACTED] GMC point estimate after the second dose of rF1V vaccine with CpG 1018 to that after the second dose of rF1V vaccine.

Criteria for secondary objectives are GMC and seroconversion rate point estimates from rF1V vaccine with CpG 1018 to meet or exceed results from rF1V vaccine at relevant visits.

Data from Part 1 subjects and Part 2 subjects will be combined to evaluate the Part 2 objectives. No multiplicity adjustment is proposed as the Part 1 objectives are not evaluated against the 3-dose regime control group.

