4.0 SAMPLE SIZE CONSIDERATIONS

Part 2 primary objective 1 is to assess the utility of a 2-dose schedule of rF1V vaccine with CpG 1018 as measured by reduction in time to onset of predicted rF1V protection. The predicted protection will be based on a [REDACTED] meter threshold. Previous animal studies have established protective efficacy in animals. Since a human efficacy study is not feasible, an immunobridge from animal data to human data via the [REDACTED] test will be used to predict the protective efficacy in humans using a regression model. An initial predicted protection threshold will be calculated based on the data generated in this study in Group 3 after 3 doses of rF1V vaccine. Once the threshold is identified, it will be applied to the study groups to evaluate the Part 2 objectives. In addition to the previous animal studies conducted to establish protective efficacy, a new animal model utilizing rF1V vaccine with CpG 1018 will be developed to establish the protective level of antibody for CpG 1018 containing vaccines. Additional analyses will include a predicted protection threshold that will be calculated based on the data generated under the new animal model after 2 doses of rF1V vaccine with CpG 1018. In both instances, the animal-to-human immunobridge and the identification of the predicted protection thresholds will be documented in a separate report.

A similar approach was used to analyze the previous Phase 2a (NCT00332956) and Phase 2b (NCT01122784) study data using the animal model from the previous animal studies. Thresholds that corresponded to 50% predicted protective efficacy in humans were established for those trials. In a pooled analysis of these previous immunobridge studies, 93% (95% Clopper Pearson confidence interval [CI] = 85%, 98%) of subjects reached the predicted protection threshold.

It is assumed that a similar percentage of the subjects in Group 3 will reach the threshold identified in this study. When this threshold is applied to both Part 2 study groups, a similar lower bound of the 95% CI is desired across the groups. Table 4-1 shows the lower bound of 95% Clopper Pearson CI for different observed levels of predicted protection assuming 85 of the 90 planned subjects (Part 1 N = 20 and Part 2 N =70) will have data available for the evaluation. Thus, with a predicted protection level of 93%, the lower bound of the 95% CI would be 85%.

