8.0 STATISTICAL METHODS

This is a phase 2, randomized, active-controlled, observer-blinded, multicenter trial of the immunogenicity, safety, and tolerability of rF1V vaccine with CpG 1018 compared with rF1V vaccine alone in adults.

Part 1 objectives will be evaluated descriptively. The administration method of vaccine utilized in Part 2 of the study will be selected by Dynavax in consultation with the Department of Defense (DoD) after Day 57 immunogenicity data become available to determine whether the GMC 1 month after 2 doses of rF1V vaccine with CpG 1018 using the selected administration method is at least 2 times higher than that 4 weeks after 2 doses of rF1V vaccine in Group 3.

The proposed statistical planning for Part 2 is presented according to the objectives. Data from Part 1 and Part 2 will be combined to evaluate the Part 2 objectives. No multiplicity adjustments are made, and all statistical tests will be conducted at 5% two-sided Type I level unless otherwise specified. All confidence intervals are two-sided 95% confidence intervals unless otherwise specified.

All analyses of demographics and baseline characteristics, medical history, vaccine exposure and safety will be summarized in a descriptive manner. In general, continuous variables will

be summarized by number of subjects, mean, standard deviation, median, quartiles, minimum and maximum, and categorical variables will be summarized by number and percentage of subjects in each study group as appropriate. All data processing, summarization, and analyses will be performed using SAS Version 9.4 or higher. Specifications for tables, graphs, and data listings will be provided in the tables, figures, listings (TFL) specifications document as needed. No specific safety hypotheses will be tested.

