Estimand: Percentage of subjects reaching the [REDACTED] threshold and associated 95% two-sided Clopper-Pearson confidence intervals will be computed. Fisher's exact tests will be used to compare predicted protection rate between study groups.

Criterion for evaluation: Similar percentage of subjects reaching the [REDACTED] threshold that corresponds to 50% predicted vaccine efficacy after 2 doses of rF1V vaccine with CpG 1018 as compared to that after 3 doses of rF1V vaccine.

Part 2 Primary Objective 2: To assess the serum [REDACTED] concentration to rF1V vaccine with CpG 1018 compared with rF1V vaccine 28 days after the second dose of vaccine

Endpoint: Ratio of geometric mean ELISA concentration (GMC) between rF1V vaccine with CpG 1018 and rF1V vaccine at Week [REDACTED].

Estimand: GMCs and associated two-sided 95% confidence intervals will be computed by exponentiating the mean and associated Student's t confidence interval of the log10 transformed individual antibody concentrations assuming Normal distribution. The ratio of GMCs and associated two-sided 95% confidence interval will be compared between rF1V vaccine with CpG 1018 and rF1V vaccine, using ANOVA if site can be used as an adjustment factor in the model or Student's t method.

Criterion for evaluation: 2-times increase in [REDACTED] GMC point estimate after the second dose of rF1V vaccine with CpG 1018 to that after the second dose of rF1V vaccine.

Part 2 Secondary Objective: To assess the serum [REDACTED] concentration to rF1V with CpG 1018 at selected time points after each dose

Endpoint: GMC and seroconversion rate of serum rF1V [REDACTED] titers at the following selected time points after each dose of vaccine:

- [REDACTED]

- [REDACTED]

[figure not shown]
Seroconversion is defined as the presence of detectable antibody in subjects who had no detectable antibody levels at Day 1, or a 2: 2-fold increase in antibody level in subjects who had detectable antibody levels at Day 1.

Estimand: GMCs and associated two-sided 95% confidence intervals will be computed by exponentiating the mean and associated Student's t confidence interval of the log10 transformed individual antibody concentrations assuming Normal distribution.

Seroconversion rate and associated 95% two-sided Clopper-Pearson confidence intervals will be computed.

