Criteria for evaluation: GMC and seroconversion rate point estimates from rF1V vaccine with CpG 1018 to meet or exceed results from rF1V vaccine at relevant visits.

Part 2 Exploratory Objective 1: [REDACTED]

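### The Part 2 secondary immunogenicity criterion compares raw point estimates, and the only between-arm interval planned near it is the GMC ratio 28 days after dose 2

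*SAP*

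**What the plan says.** The endpoint in SAP 8.6 (Part 2 Secondary Objective) is "GMC and seroconversion rate of serum rF1V [REDACTED] titers at the following selected time points after each dose of vaccine". The list that follows is redacted.

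The criterion is "GMC and seroconversion rate point estimates from rF1V vaccine with CpG 1018 to meet or exceed results from rF1V vaccine at relevant visits". Protocol 11.4 has the same rule: "Criteria for secondary objectives are GMC and seroconversion rate point estimates from rF1V vaccine with CpG 1018 to meet or exceed results". It also appears in the protocol synopsis, Protocol Section 3 and SAP 3.0.

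The analysis described under this objective is per arm. GMCs come with Student's t intervals on "log10 transformed individual antibody concentrations assuming Normal distribution", and for the other measure "Seroconversion rate and associated 95% two-sided Clopper-Pearson confidence intervals will be computed". No ratio, difference or margin is given there.

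Elsewhere in SAP 8.6, the Part 1 primary objective and Part 2 Primary Objective 2 each specify a GMC ratio with a two-sided 95% CI, both 28 days after the second dose. SAP 8.8 plans no further analyses.

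**The concern.** The criterion asks whether one estimate is at least as large as another. It cannot separate a real shortfall from sampling noise, and a better-than-control estimate meets it however imprecise that estimate is.

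This sits awkwardly with the protocol's stated aim. Protocol 2.4.2.1.1 says the project seeks a response that is non-inferior or superior on a shorter schedule. The same section calls peak GMCs of 341.6 and 352.1 mIU/mL in the hepatitis B programme similar; their ratio is 341.6/352.1 = 0.97. A meet-or-exceed rule applied to those two numbers would record a failure. They are peaks, not a same-visit comparison, so this is only an illustration.

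The comparison is most delicate after control's third dose. There the two-dose CpG regimen faces a three-dose regimen, and near-equality or a modest deficit is a plausible result. A reader would want to know how large a deficit the data can exclude, and the readable plan has no interval that answers this.

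**Working it through.** **Inputs from the documents**
- Evaluable subjects: SAP 4.0 works from "assuming 85 of the 90 planned subjects (Part 1 N = 20 and Part 2 N =70) will have data available for the evaluation". That figure is given for predicted protection; I apply it to the secondary endpoint.
- Allocation: Protocol 4.3, "In Part 2, subjects will be randomized 1:1 to 1 of 2 groups". Hence 85 per arm.
- Decision rule: CpG estimate ≥ control estimate, with ties counting as met.

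**Assumed, because the documents do not give them:** log10 SD (0.4–0.6, wider range 0.3–0.8), true seroconversion rate (80–99%), number of visits and correlation between visits.

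**Step 1. The plan's own figure.** SAP Table 4-1 gives Clopper-Pearson limits at N=85. Exact limits are:
- 81/85: 88.4–98.7%
- 79/85: 85.3–97.4%
- 77/85: 82.3–95.8%

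All three agree with the table after rounding. No operating characteristic is stated for the secondary criterion.

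**Step 2. GMC at one visit.** With true ratio R,

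P(met) = Φ( log10 R / (SD × √(2/85)) ), where √(2/85) = 0.1534.

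For R = 0.9 and SD = 0.4: log10 0.9 = −0.0458, SE = 0.0614, z = −0.746, P = 22.8%.

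| True ratio | SD 0.4 | SD 0.5 | SD 0.6 |
|---|---|---|---|
| 0.8 | 5.7% | 10.3% | 14.6% |
| 0.9 | 22.8% | 27.5% | 31.0% |
| 1.0 | 50% | 50% | 50% |
| 1.1 | 75.0% | 70.5% | 67.4% |
| 2.0 | >99.9% | >99.9% | >99.9% |

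At R = 1 the answer is 50% whatever the SD. Over SD 0.3–0.8, R = 0.9 gives 16–35%. At R = 2 the lowest value is 99.3% (SD 0.8).

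**Step 3. Seroconversion at one visit, equal true rates.** By symmetry P(fail) = (1 − P(tie))/2, with P(tie) = Σ p(x)² over the Binomial(85, π) probabilities.

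| True rate π | P(tie) | P(fail) |
|---|---|---|
| 80% | 7.7% | 46.2% |
| 93% | 12.1% | 44.0% |
| 95% | 14.2% | 42.9% |
| 98% | 22.8% | 38.6% |
| 99% | 34.1% | 33.0% |

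The result is sensitive to small imbalances. With 83 and 85 evaluable subjects, failure ranges from 33% to 57% over rates of 93–99%, depending on which arm is smaller.

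**Step 4. How the unstated parts of the rule matter (equal arms).**
- If both measures must be met at one visit, simulation gives P(both met) of 27–40% for rates of 80–99%. The low end treats the measures as independent; the high end derives both from the same titre.
- If GMC must be met at every visit, P(met) at correlation 0.5 to 0.9 is 33–43% for two visits, 25–39% for three and 20–37% for four.

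**Step 5. What an interval would add.** At 85 per arm, the 95% CI for the GMC ratio is the estimate multiplied and divided by 10^(1.96 × SD × 0.1534): a factor of 1.32, 1.41 or 1.51 at SD 0.4, 0.5 or 0.6. For the seroconversion difference, 1.96 × √(2π(1−π)/85) gives about ±7.7 points at π = 93% and ±4.2 points at 98%.

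**The case against.** The other side has several fair points.

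- **Visits.** A reader might infer that the visits are unnamed and will be picked later. The documents do not support that. A list of time points is present but redacted, it may already separate visits before and after the third injection, and no readable text defers the choice. What stands is narrower: the readable text does not tie the relevant visits to the list, or say whether the rule applies at all or any visits, or to both or either measure.
- **Intervals.** It is tempting to say that the trial plans no between-arm interval. That is wrong, because the GMC ratio with its CI is planned 28 days after dose 2. Per-arm intervals are also planned for both measures. Two per-arm intervals do not replace an interval for the contrast, and none is visible for seroconversion or for GMC at other visits.
- **Relevance.** At the key visit the plan looks for a two-fold GMC ratio, and there the rule almost never misfires. This stands, and confines the concern mainly to other visits.
- **Status.** This is a secondary, descriptive benchmark in a phase 2 trial, with no test attached and no readable decision tied to it. The SAP 8.0 statement "No multiplicity adjustments are made, and all statistical tests will be conducted at 5% two-sided Type I level unless otherwise specified" governs tests and does not bear on it. This lowers the stakes, but the criterion is still pre-specified and will be reported as met or not met.

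**Conclusion.** The point holds within limits. Under the Part 2 secondary objective the criterion rests on point estimates alone, and the readable analysis has no between-arm contrast. With 85 per arm and truly equal arms, GMC fails 50% of the time per visit regardless of SD; seroconversion fails about 33–43% at assumed rates of 95–99%. A true ratio of 0.9 passes 23–31% of the time at an assumed log10 SD of 0.4–0.6. The consequence falls mainly on visits other than 28 days after dose 2, above all after control's third dose.

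Three stronger readings go too far:
- That failure is about one half for both measures: this is exact only for GMC.
- That the overall result can be put at a single low probability across visits: this needs a visit count, a correlation and an every-visit rule, none of which the readable text gives. The multi-visit figures are illustrations.
- That the outcome is mostly chance: this is so only when the arms are close.

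The redacted exploratory text could contain further contrasts, so the statement is limited to what can be read.

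**What to change.** In SAP 8.6 and Protocol 11.4, and wherever the criterion is repeated:

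- At each listed time point, report the GMC ratio with a 95% CI from the same model as Primary Objective 2 (ANOVA with site if usable, otherwise Student's t).
- At each listed time point, report the seroconversion difference with a 95% Newcombe or Miettinen-Nurminen CI.
- Interpret the secondary criterion from these intervals, not from point estimates alone.
- Link the criterion to the listed time points. If any benchmark wording stays, say whether it applies at all or any of them, and to both or either measure.
- Present visits before and after the third injection separately, if the redacted list does not already do so.

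The cost is SAP and protocol wording and a few more table columns, using data already collected. The downside is the loss of a simple pass/fail line.

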8.7 Safety Analyses

Vaccine exposure and compliance will be summarized descriptively for safety population.

Safety data will be analyzed descriptively and will be based on the safety population. The safety parameters will be presented for all sites combined. Summary statistics will be used to describe the incidence of all post-injection reactions (PIRs) and AEs, including SAEs, deaths, acute myocardial infarctions (AMIs), and AESIs. AMIs include the events with PTs of Acute Myocardial Infarction, Acute Coronary Syndrome, or Myocardial Infarction. The incidence and proportion of post-injection reactions and AEs will be summarized. AEs will be coded using the MedDRA SOC and PT.

The treatment-emergent period is defined in [Section 6.1](#).

On Day █ Day █, and Day █, subjects will be asked to complete an e-diary (or equivalent) to record any solicited local and systemic reactions during the 7-day follow-up period after vaccination. Post-injection reactions persisting beyond 7 days after injection are considered to be AEs and need to be recorded and reported as AEs (see protocol Section 10.2). The severity of the post-injection reactions will be graded using the United States Food and Drug Administration's (FDA) Guidance for Industry: Center for Biologics Evaluation and Research (CBER) Toxicity Grading Scale for Healthy Adult and Adolescent Volunteers Enrolled in Preventive Vaccine Clinical Trials.

Local reactions include pain, redness, pruritus and swelling, and systemic reactions include fatigue, temperature, chills, malaise, myalgia, vomiting, diarrhea, and headache.

Post-injection reactions reported from day 1 to day 7 will be summarized by maximal severity and by vaccine group. The severity of local reactions, including redness and swelling will be categorized as none (:S25mm), >25 to :S50mm (mild), >50 to :S100mm (moderate) and >100mm (severe).

The severity of local reactions including pain, and pruritus and systemic reactions including fatigue, chills, malaise, myalgia, vomiting, diarrhea and headache occurring up to 7 days after each vaccination will be categorized as none, mild (no interference with activity), moderate (some interference with activity), severe (significant, prevents daily activity).

Temperature will be categorized as <38°C (no fever), 38-38.4°C (mild), 38.5-38.9°C (moderate), 39-40°C (severe) and >40°C (life threatening).

Each local and systemic reaction will also be categorized as none vs. any.

All AEs will be coded to preferred term and system organ class. An AE that started or increased in severity during the treatment-emergent period will be considered a TEAE. The severity of AEs and laboratory abnormalities will be graded based on CBER Toxicity Grading Scale for Healthy Adult and Adolescent Volunteers Enrolled in Preventive Vaccine Clinical Trials, with the modification that, by convention, all fatal AEs will be graded as Grade 5 (Fatal). All AEs not listed in the CBER toxicity grading scale will be graded as shown in Table 8-1.

Table 8-1: Grading Scale for Adverse Events Not Included in the CBER Guidance on Toxicity Grading for Healthy Volunteers in Vaccine Clinical Trials

AE Severity	Definition
Grade 1 – Mild	No interference with activity
Grade 2 – Moderate	Some interference with activity, not requiring medical intervention

AE Severity	Definition
Grade 3 – Severe	Prevents daily activity and requires medical intervention
Grade 4 – Potentially life-threatening	Emergency room visit or hospitalization
Grade 5	Death

A study vaccine -related TEAE is defined as any TEAE with at least a possible relationship to the study vaccine as assessed by the investigator.

Subjects with multiple occurrences of events for a given preferred term, system organ class, or overall will only be counted once at the worst severity and strongest relationship to study vaccine for each PT, SOC, and overall, respectively. AEs that are continuous but change in grade, relationship, or seriousness will be counted as 1 event. TEAEs of unknown severity will be categorized separately. A TEAE of unknown relationship will be categorized separately.

Incidence and percentages of subjects experiencing each reaction will be presented by severity. Summary tables showing the occurrence of any local or systemic reaction overall and at each time point will also be presented.

Tabular summaries including numbers and percentages of the following adverse events will be provided:

- All TEAEs
- TEAEs of Grade 3 or above
- All treatment-related AEs
- Treatment-related AEs of Grade 3 or above
- All treatment-emergent SAEs
- All treatment-related SAEs
- All TEAEs leading to premature discontinuation of study vaccine
- All SAEs leading to death
- All AMI
- All AESI

Listings will be provided for all TEAEs.

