10.2 Definition of Post-Injection Reactions

Post-injection reactions persisting beyond 7 days after injection are considered to be AEs and need to be recorded and reported as AEs. The severity of the post-injection reactions will be graded using the Toxicity Grading Scale for Healthy Adult and Adolescent Volunteers Enrolled in Preventive Vaccine Clinical Trials ([Appendix 2](#)).

Certain local and systemic events are routinely monitored in vaccine clinical trials as indicators of vaccine reactogenicity. It is recognized that each of these events, and particularly those of systemic nature, may under certain circumstances, in an individual subject, have a cause that is unrelated to study vaccine. However, as a matter of convenience and in accordance with common clinical practice, such events occurring within a specified period of time after immunization are herein termed ‘post-injection reactions’ and will be considered as related to treatment.

Post-injection reactions documented by the subject will be collected via a diary, reviewed by the study nurse/coordinator with the subject and recorded appropriately.

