Pain	Does not interfere with activity	Repeated use of non-narcotic pain reliever > 24 hours or interferes with activity	Any use of narcotic pain reliever or prevents daily activity	Emergency room (ER) visit or hospitalization
Tenderness	Mild discomfort to touch	Discomfort with movement	Significant discomfort at rest	ER visit or hospitalization
Erythema/Redness ^a	2.5 – 5 cm	5.1 – 10 cm	> 10 cm	Necrosis or exfoliative dermatitis
Induration/Swelling ^b	2.5 – 5 cm and does not interfere with activity	5.1 – 10 cm or interferes with activity	> 10 cm or prevents daily activity	Necrosis
Pruritus ^c	No interference with activity	Some interference with activity, not requiring medical intervention	Prevents daily activity and requires medical intervention	ER visit or hospitalization
Systemic Reactions				
Fever (°C)	38.0 – 38.4	38.5-38.9	39.0-40	>40
Myalgia	No interference with activity	Some interference with activity	Significant: prevents daily activity	ER visit or hospitalization
Fatigue	No interference with activity	Some interference with activity	Significant: prevents daily activity	ER visit or hospitalization
Malaise	Uneasiness or lack of well being	Uneasiness or lack of well being; limiting instrumental ADL	A grade is not available	A grade is not available
Chills ^c	No interference with activity	Some interference with activity, not requiring medical intervention	Prevents daily activity and requires medical intervention	ER visit or hospitalization
Nausea/vomiting	No interference with activity or 1 – 2 episodes/24 hours	Some interference with activity or > 2 episodes/24 hours	Prevents daily activity, requires outpatient IV hydration	ER visit or hospitalization for hypotensive shock
Diarrhea	2 – 3 loose stools or < 400 gms/24 hours	4 – 5 stools or 400 – 800 gms/24 hours	6 or more watery stools or > 800gms/24 hours or requires outpatient IV hydration	ER visit or hospitalization

	Mild (Grade 1)	Moderate (Grade 2)	Severe (Grade 3)	Potentially Life Threatening (Grade 4)
Headache	No interference with activity	Repeated use of nonnarcotic pain reliever > 24 hours or some interference with activity	Significant; any use of narcotic pain reliever or prevents daily activity	ER visit or hospitalization
Systemic Illness				

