Illness or clinical adverse event (as defined according to applicable regulations)	No interference with activity	Some interference with activity not requiring medical intervention	Prevents daily activity and requires medical intervention	ER visit or hospitalization

Source: ([Center for Biologics Evaluation and Research 2007](#)).

ER = emergency room; IV = intravenous.

^a In addition to grading the measured local reaction at the greatest single diameter, the measurement should be recorded as a continuous variable.

^b Induration/swelling should be evaluated and graded using the functional scale as well as the actual measurement

^c Not part of CBER grading scale.

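### SAP 8.7 summarises solicited reactions in severity categories that do not match protocol Appendix 2: ten reactions have no Grade 4 class, swelling is classed by size alone, and malaise gains a severe class

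*SAP*

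**What the plan says.** Protocol 10.2 fixes the scale: "The severity of the post-injection reactions will be graded using the Toxicity Grading Scale for Healthy Adult and Adolescent Volunteers". The protocol prints this scale as Appendix 2, and section 9.4.4 gives the same instruction.

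SAP 8.7 also names the CBER scale. It then sets categories for the tables:

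- Pain, pruritus, fatigue, chills, malaise, myalgia, vomiting, diarrhea and headache "will be categorized as none, mild (no interference with activity), moderate (some interference with activity), severe (significant, prevents daily activity".
- Local reactions "including redness and swelling will be categorized as none" up to and including 25 mm, then mild, moderate or severe with cuts at 50 mm and 100 mm.
- Temperature alone has a further class: "39-40°C (severe) and >40°C (life threatening".

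On output, the SAP states: "Incidence and percentages of subjects experiencing each reaction will be presented by severity". Each reaction is also summarised as none versus any.

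Appendix 2 grades redness at Grade 4 as "Necrosis or exfoliative dermatitis", grades swelling at Grade 3 as "> 10 cm or prevents daily activity", and adds in footnote b: "Induration/swelling should be evaluated and graded using the functional scale as well as the actual measurement".

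**The concern.** A programmer cannot follow both instructions in SAP 8.7. The first points to a four-grade scale with its own criteria for most reactions. The second stops at severe for every reaction except temperature and uses one generic activity scale for nine of them.

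Reactogenicity is a secondary safety endpoint in both parts, and protocol 2.4.2 says there are no clinical data on adding CpG 1018 to rF1V. The severity tables are where a reader will look for the worst reactions. Built literally from SAP 8.7, they would not show the grades that the protocol requires. They also could not be checked against protocol 5.3 and 8.2, which use Grade 4 and Grade 3-or-higher reactions.

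**Working it through.** There is no plan figure to reproduce. The check is a row-by-row comparison of the reactions listed in SAP 8.7 with Appendix 2. SAP temperature is compared with the fever row and SAP vomiting with the nausea/vomiting row.

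**Denominator.** 4 local (pain, redness, pruritus, swelling) + 8 systemic (fatigue, temperature, chills, malaise, myalgia, vomiting, diarrhea, headache) = 12.

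| Reaction | Grade 4 in Appendix 2 | SAP class above severe | Grades 1-3, SAP against Appendix 2 |
|---|---|---|---|
| Swelling | yes | no | differs: functional criterion absent |
| Malaise | no | no | differs: SAP has severe, Appendix 2 stops at Grade 2 |
| Pain | yes | no | differs if literal: analgesic and narcotic use absent |
| Headache | yes | no | differs if literal: analgesic and narcotic use absent |
| Vomiting | yes | no | differs if literal: episode count and IV hydration absent |
| Diarrhea | yes | no | differs if literal: stool count, weight and IV hydration absent |
| Pruritus | yes | no | differs if literal: need for medical intervention absent |
| Chills | yes | no | differs if literal: need for medical intervention absent |
| Redness | yes | no | differs only at exactly 25 mm (none in SAP, Grade 1 in Appendix 2) |
| Temperature | yes | yes | matches |
| Fatigue | yes | no | matches |
| Myalgia | yes | no | matches |

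**Grade 4.** Defined for 12 − 1 (malaise) = 11. The SAP has a class for 1 (temperature). Without a class: 11 − 1 = 10, made up of 8 on the activity scale and 2 on the size scale (redness, swelling).

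**Grades 1-3.** 2 differ under any reading (swelling, malaise), 6 differ only on the literal reading, 1 differs at a boundary point and 3 match: 2 + 6 + 1 + 3 = 12. On the literal reading, 2 + 6 = 8 of 12 differ in substance.

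**Constructed cases.**
- A 20 mm swelling that prevents daily activity: Appendix 2 Grade 3, SAP none. It also changes the none-versus-any count.
- A 30 mm redness with necrosis: Appendix 2 Grade 4, SAP mild.
- Six watery stools without interference with activity: Appendix 2 Grade 3, SAP mild on the literal reading only.

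**The case against.** The strongest reply is that grading and display are separate steps. The SAP first says reactions are graded on the CBER scale. The bracketed activity phrases may then be short labels for grades already assigned. On that reading the differences for pain, headache, vomiting, diarrhea, pruritus and chills largely disappear. This stands, so a reader who takes eight of twelve as an unconditional count goes further than the text allows. The reply does not supply a class for Grade 4, explain a severe malaise class, or turn millimetre cut-offs for swelling into a functional grade.

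A second reply is that Grade 4 reactions would surface elsewhere. A reader might infer from the missing class that they disappear from the report, and the documents do not support that. On the activity scale they would most naturally be counted within severe: less visible, not lost. SAP 8.7 also tabulates TEAEs leading to discontinuation of study vaccine, and protocol 5.3 lists a Grade 4 reaction within 7 days among the AEs that end a subject's dosing. A reaction leading to hospitalisation could appear among the SAEs.

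These tables are still not a dependable substitute:

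- Protocol 9.4.4 and 10.2 make a reaction an AE when it persists beyond 7 days, whereas 5.3 and 10.1 treat some solicited reactions as AEs without that condition. The documents do not settle the status of shorter reactions.
- A reaction after the last dose would not enter the discontinuation table.
- Emergency room visits, which are part of most Grade 4 definitions, do not count as hospitalisation under protocol 10.9.1. Section 10.9.2 limits that exclusion to visits under 24 hours.

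Finally, safety is descriptive with no hypotheses tested, and the table specifications are a separate document that may already contain a Grade 4 column. Both points are fair and limit the weight of the finding.

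**Conclusion.** SAP 8.7 is wrong as written and should be corrected. Three points are firm: no Grade 4 class for 10 of the 11 reactions that have a Grade 4 (with necrotic redness or swelling classed by diameter), swelling classed on size alone, and a severe malaise class without an Appendix 2 grade. The wider count of 8 of 12 depends on taking the bracketed SAP wording as the operative definition.

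The effect is confined to descriptive severity tables and a few none-versus-any counts at the edges (redness at exactly 25 mm, and swelling at 25 mm or with functional interference at or below that size). A reader might infer an effect on dosing or stopping decisions, but protocol 5.3 and 8.2 act on reactions under the protocol and do not use the SAP tables. Alpha and power are untouched. The documents give no frequency for the affected cases, so the net shift is unknown.

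**What to change.** Reconcile SAP 8.7 with Appendix 2, and cite Appendix 2 itself as the scale, because its footnote c says the pruritus and chills rows are not part of the CBER scale. Suggested text in place of the category paragraphs:

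> Each solicited reaction is tabulated by maximum protocol Appendix 2 grade: none, 1, 2, 3, 4 (malaise: none, 1, 2). Swelling is graded on both size and function per Appendix 2 footnote b. Reactions reported but meeting no Appendix 2 grade definition (for example pruritus or chills that prevent activity without medical intervention, or malaise beyond Grade 2) are shown in a separate row, 'reported, not gradable under Appendix 2', and count as 'any'.

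In addition:

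- Keep explicit definitions of none: temperature below 38°C; redness below 25 mm, so that 25 mm falls in Grade 1; swelling below 25 mm and without functional interference.
- Add a Grade 4 column and a 'Grade 3 or higher' row.
- Footnote any Appendix 2 element that the diary or eCRF did not capture, such as narcotic use, stool count or functional swelling grade.

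The cost is SAP wording and table shells, plus the extra row for ungradable reactions. This assumes that the diary and eCRF hold the grades that protocol 9.4.4 already requires. Those fields are not in the documents. Where an element is missing, the footnote is the cost.
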